Comparison of the Efficiency of Femur Nerve Block and Intravenous Analgesia Treatment in Hip Fracture Patients

MATERIALS AND METHODS

Design and Setting

This was a prospective, double-blind, randomized, single-center superiority trial with a 1:1 parallel-group design, conducted in an academic ED. Ethical approval for this study was obtained from the local ethics committee and the institutional review board (approval no: 09.2022.604, Marmara University Faculty of Medicine Clinical Research Ethics Committee). The study was conducted in accordance with the ethical standards of the Declaration of Helsinki and relevant local regulations. We used the CONSORT checklist when writing our report.

Study Population, Inclusion, and Exclusion Criteria

All consecutive adult patients (aged ≥ 18 years) presenting to our ED between November 2022 to December 2024 with a radiologically verified hip fracture were screened for inclusion based on the following criteria: (i) diagnosed with a unilateral fracture of the femoral neck or proximal femur via radiological evaluation; (ii) provision of informed consent by the patient, a relative, or a legal guardian.

The exclusion criteria were as follows: (i) hemodynamic instability or requiring urgent intervention for trauma; (ii) concomitant fractures; (iii) INR ≥ 2.5 or at risk of hemorrhage; (iv) received analgesics or a nerve block to the affected area prior to arrival at the ED; (v) allergy to local anesthetic agents or fentanyl; (vi) pregnancy; (vii) periprosthetic fracture; (viii) peripheral neuropathy.

Randomization and Allocation Concealment

Patients who met the inclusion/exclusion criteria were enrolled and randomly assigned in a 1:1 ratio to receive either FNB or fentanyl therapy. Randomization was performed using a computer-generated sequence with blocks of six to ensure a balanced allocation of groups. The allocation sequence of patients was concealed using consecutively numbered and sealed envelopes. A non-blinded investigator performed the randomization.

Masking

In accordance with the methodology of the study, the attending physician, nurses, treatment team, and participants were blinded using the following protocol:

To blind the treatment allocation, each participant was administered intravenous (IV) treatment and femoral nerve injection concurrently, with one group receiving a placebo in lieu of the IV analgesic and the other group receiving a placebo in place of the FNB. FNB was administered as 20 mL of 0.5% bupivacaine or a placebo (20 mL of 0.9% normal saline) filled into a syringe.

The intravenous analgesic was administered as fentanyl at a dosage of 1 mcg/kg. (This was created by drawing 100 mcg of fentanyl into the syringe and diluting it with 100 mL of 0.9% sodium chloride solution.) The placebo consisted 100 mL of 0.9% normal saline solution.

Syringes and serum set for FNB and IV treatment were prepared by a non-blinded investigator according to the instructions. The syringes were labeled with the designations "Syringe A" and "Syringe B," while the serum sets were labeled "Set A" and "Set B." Syringes and sets prepared with application instructions were given to the team administering the treatment according to the randomization order (A or B). The application instructions delineated the protocol for the administration of FNB and IV treatment, enumerating the sequence in which the respective procedures were to be executed. For example, "Initially, administer the medication in syringe B for FNB." Administer the drug in Set B for intravenous analgesic treatment at a dosage of 1 cc per kilogram to the patient.

Data Collection

Vital signs, chronic diseases and demographic data about the patients were documented at the time of admission. Pain scores were recorded by nurses, blinded to the treatment groups, just before to the initiation of therapy and 20 minutes post-treatment completion.

Cognitive functions of participants were evaluated utilizing the Glasgow Coma Scale (GCS) and the Abbreviated Mental Test 4 (AMT-4). The Numeric Pain Rating Scale (NPRS) was employed for patients capable of verbally rating their pain (GCS was 15 and AMT-4 ≥ 8) on a scale of 0 to 10, whilst the Pain Assessment in Advanced Dementia Scale (PAINAD) was utilized to evaluate pain in individuals with cognitive impairment (GCS < 15 or AMT-4 < 8). This guaranteed that all participants obtained a uniform score ranging from 0 to 10.

We also followed whether patients needed rescue analgesia (IV fentanyl, tramadol or morphine) within four hours after the end of treatment.

FNB procedure

The femoral nerve block (FNB) was performed by three researchers who had training in this domain and a minimum of two years of practical experience in its implementation.

Patients were placed in the supine position. Following preparation and the administration of local anesthesia, 20 mL of 0.5% bupivacaine or 20 mL of 0.9% normal saline as a placebo was injected into the region utilizing a high-frequency linear probe under ultrasound guidance. The nerve was recognized as an echogenic triangular region lateral to the femoral vein. An ultrasonic needle sized 22G x 50 mm (SonoPlex STIM; PAJUNK GmbH, Geisingen, Germany) was placed by the Seldinger technique until its tip was positioned near to the femoral nerve. Following the confirmation of negative aspiration, a small-volume injection was administered, and the expansion of the nerve sheath was visualized on the monitor as the fluid infused. Subsequently, the entire 20 mL was administered to finalize the treatment. Throughout the

process, blood pressure, heart rate, respiration rate, and arterial oxygen saturation were observed.

Outcomes

The primary outcome of the study was the change in pain intensity from baseline to 20 minutes after the intervention. The secondary outcomes included the need for rescue analgesia and the occurrence of adverse events.

Sample size estimation

The sample size was calculated to obtain a statistically significant difference between the two groups in the change in the pain scale at 20 minutes after treatment, which was our primary endpoint in comparing the analgesic efficacy of FNB and IV opioids in patients with hip fractures. To demonstrate this difference with 90% power, we determined the sample size to be 52 for each group, totaling 104, based on calculations from previous studies. Calculations were made with the G*Power program (Universitat Düsseldorf)

Statistical analysis

Analyses were conducted on an intention-to-treat (ITT) basis; subgroup analysis were also reported for comparison. No data was missing for the primary outcome. Baseline continuous variables were presented as mean (SD) or median (IQR), and categorical variables as n (%). The between-groups differences were calculated using the change of each group and reported as mean or median differences with 95% confidence intervals (CI). We considered differences statistically significant if the 95% CI did not cross zero. Effect sizes of differences and ratios were reported with their 95% CI. The accepted Type 1 error in this study was 5%. Graphs were produced using GraphPad Prism 10.4.1 (GraphPad Software Inc., San Diego, California). Statistical analyses were performed using Jamovi version 2.3.26 (The Jamovi Project, Australia).

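### A single block size of six leaves about a quarter of assignments certain to anyone who knows it and all past allocations, and the plan does not say such a person was kept out of eligibility decisions

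*Combined protocol and SAP*

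**What the plan says.** The Design and Setting section describes a "prospective, double-blind, randomized, single-center superiority trial with a 1:1 parallel-group design". Under Randomization and Allocation Concealment, eligible patients are "randomly assigned in a 1:1 ratio to receive either FNB or fentanyl therapy", and the method is given as "Randomization was performed using a computer-generated sequence with blocks of six to ensure a balanced allocation of groups". No other block size and no stratification factor is mentioned. On concealment the section says: "The allocation sequence of patients was concealed using consecutively numbered and sealed envelopes". It then says: "A non-blinded investigator performed the randomization".

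Under Masking, "the attending physician, nurses, treatment team, and participants were blinded using the following protocol", and the scheme that follows is a double dummy. Its materials also come from an unblinded role: "Syringes and serum set for FNB and IV treatment were prepared by a non-blinded investigator according to the instructions". Whether this is the person who randomises is not stated.

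Exclusion (iii) in the Study Population section reads "INR ≥ 2.5 or at risk of hemorrhage". The first half is a laboratory limit. The second half has no definition.

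The documents do not say who judged eligibility or obtained consent, who held the list and the envelopes, or whether the unblinded investigator was kept away from screening.

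**The concern.** A sealed envelope hides the next allocation only from someone who cannot work it out from the previous ones. With one list, one centre and a constant block of six, the rest of a block is determined once either arm has used its three places. The person who randomises, and the person who fills the syringes and infusion sets, are both placed to know what earlier patients received.

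Foreknowledge does harm only if it can influence who enters or when. The bleeding-risk half of exclusion (iii) is a point where it could. A patient with an INR below 2.5 passes the numerical limit and can still be kept or excluded on judgement. If the person making that judgement could foresee the arm, the groups could come to differ in bleeding risk, frailty or baseline pain. Masking acts after entry and would not correct this. The Statistical analysis section compares changes between groups and describes no covariate adjustment that might reduce such a difference.

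**Working it through.** **Inputs.** Block size 6, ratio 1:1 and one centre come from the Design and Setting and Randomization sections. The total of 104 comes from Sample size estimation. The plan gives no predictability figure of its own to reproduce.

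**Assumption about the observer.** The observer knows the block size and every earlier allocation.

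**Assignments known with certainty.** A 3+3 block has C(6,3) = 20 equally likely orders. A position is forced when one arm has already used its three places.

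- Positions 1 to 3: never forced.
- Position 4: forced if the first three are all one arm, 2/20 = 10%.
- Position 5: forced if the first four split 3–1, 8/20 = 40%.
- Position 6: always forced, 100%.

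The sum is 0.1 + 0.4 + 1.0 = 1.5 per block. The closed form 2m/(m+1) with m = 3 places per arm also gives 1.5. As a share, 1.5/6 = 25%.

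For 104 patients there are 17 full blocks and 2 further patients, because 17 × 6 = 102. The expected number forced is 17 × 1.5 + 0 = 25.5, and 25.5/104 = 24.5%.

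**Best guess.** The observer always names the arm with more places left. The chance of being right, by position, is 0.5, 0.6, 0.6, 0.7, 0.7 and 1.0. The sum is 4.1, and 4.1/6 = 68.3%, against 50% by chance.

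**Effect of varying the block size.** In 1,500 simulated lists of 104, the observer knows the set of sizes and all earlier allocations, but not the order of the sizes.

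| Block sizes | Certain | Best guess right |
|---|---|---|
| 6 only | 24.5% | 68.0% |
| 4, 6 | 5.5% | 69.2% |
| 4, 6, 8 | 2.2% | 67.9% |

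The first row agrees with the exact results for 104 patients: 25.5/104 = 24.5%, and (17 × 4.1 + 0.5 + 0.6)/104 = 70.8/104 = 68.1%. Varying the size removes nearly all certainty and leaves the guessing advantage almost unchanged.

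**What a check on existing data could detect.** About 25 forced positions give roughly 13 patients per arm. At 80% power and two-sided 5%, the detectable difference in baseline pain is (1.96 + 0.84) × √(2/13) = 2.80 × 0.392 = 1.1 SD. Only a very large difference would show.

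**The case against.** The strongest reply is that the step from prediction to selection is missing from the documents. To steer entry, one person must know past allocations, know the block size, and influence eligibility or timing. The plan gives the non-blinded role randomisation and kit preparation, and nothing else. It says that consecutive adults were screened and that patients were randomised after meeting the criteria. Attending physicians, nurses and the treatment team are listed as blinded. A reader might infer from the block size and the judgement clause that entry was, or readily could be, steered. The documents do not support that inference. They are silent on who judged eligibility, and silence is a gap in reporting, not evidence of overlap. This part of the objection stands.

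It also stands that the 25% applies to an informed observer only. It does not extend to blinded clinical staff if the double dummy held. One qualification concerns the kit labels A and B. If they kept one meaning throughout, the treatment team could have followed the label sequence, but the plan does not say whether they did.

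It is further fair to say that block size is the lesser issue. Varying it does little against guessing, and nothing against someone who holds the list itself. Separation of roles deals with both.

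What does not stand is that the existing safeguards settle the matter. Envelopes do not block inference from earlier allocations, masking begins after entry, and consecutive screening does not constrain an undefined exclusion.

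**Conclusion.** The concern holds as a limited one. An expected 25.5 of 104 assignments (24.5%; 25% per complete block) are certain in advance to anyone who knows the block size and all earlier allocations, and such a person's best guess is right about 68% of the time. This assumes one unstratified list with every block of size six, as the text reads. The investigator who randomises and the one who prepares the kits are placed to know the earlier allocations. Whether either knew the block size, or had any say in eligibility, is not stated.

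Selection by expected arm is therefore a risk that the plan leaves open, not one that it shows. No size can be put on any resulting bias, because the documents do not say how often the bleeding-risk clause was applied or by whom. A better arrangement is available at little cost, so the change is worth making even though no harm is demonstrated.

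**What to change.** **First, separate the roles.** A blinded clinician already on the team records and times the eligibility decision, with the reason for any exclusion under the bleeding-risk clause, before the non-blinded investigator opens the envelope. That investigator takes no part in screening. This protects against both certainty and guessing.

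**Second, vary the block size.** Generate the list with randomly varying sizes, for example 4, 6 and 8, not disclosed to the investigators. On its own this removes certainty and not the guessing advantage, so it comes second.

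**Cost.** A new list and a short timed eligibility record are needed, with no extra staff. The plan describes no eligibility form at present; the only checklist it names is CONSORT, for the report. The downside is a final imbalance of a few patients. Stopping part-way through a block of 8 can leave the arms up to 4 apart. Exact balance is not guaranteed now either: 104 = 17 × 6 + 2, so the arms can differ by 2.

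**For patients already enrolled.** The text is in the past tense and gives a recruitment period ending in December 2024, so both steps may come too late for this trial. In that case, report who judged eligibility, whether they could see allocations or knew the block size, who held the list and envelopes, how the bleeding-risk clause was applied, and whether labels A and B had a constant meaning. If the roles were separate, one sentence settles the point; if they were not, state it as a limitation. Any comparison of baseline pain in the roughly 25 forced positions should be descriptive only, since a null result there would reassure little.

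### Subgroup results are reported under a rule that judges each 95% CI on its own, with no interaction estimate, so they can suggest a difference in effect where there is none

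*Combined protocol and SAP*

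**What the plan says.** All of this is in the combined protocol and SAP.

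- **Subgroups.** The first sentence of Statistical analysis states the intention-to-treat basis and then adds "subgroup analysis were also reported for comparison". It names no factor, cut-point or number of subgroups. It gives no interaction test, no multiplicity control and no exploratory label.
- **Estimate.** "The between-groups differences were calculated using the change of each group and reported as mean or median differences with 95% confidence intervals". No regression model is described, so no interaction term arises by default.
- **Decision rule.** "We considered differences statistically significant if the 95% CI did not cross zero". This is the only rule given, and it is not limited to the primary comparison. The section also sets the type I error at 5%.
- **Power.** Sample size estimation concerns the overall comparison only: "To demonstrate this difference with 90% power, we determined the sample size to be 52 for each group, totaling 104". The effect and SD are not given; the figure is said to be "based on calculations from previous studies".

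**The concern.** A CI within one subgroup tests whether the effect there is zero. It does not test whether the effect differs from that in another subgroup. When two subgroups have the same true effect and limited power, it is common for one CI to exclude zero and the other to include it, and readers tend to take that pattern as effect modification.

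Naming the subgroups in advance would not cure this, because a named list analysed under the same rule gives the same patterns. At stake is a report that the block works in one kind of patient and not in another when the data show no such thing. With only 104 patients, every subgroup has less power than the trial as a whole.

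**Working it through.** **Inputs from the documents.** 52 per group, 104 in total, 90% power (Sample size estimation); 5% type I error and the 95% CI rule, which is equivalent to a two-sided 5% test (Statistical analysis); 1:1 allocation (Randomization and Allocation Concealment); no missing primary data (Statistical analysis), so no dropout allowance.

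**Inputs assumed.** The standardised effect d, a two-sided t-test, and two-level subgroups split 26/26, 36/16 or 42/10 per arm.

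**Step 1: the plan's own figure.** 52 per group cannot be reproduced because no effect or SD is stated. It can only be solved backwards. By the normal approximation, d = (1.960 + 1.282) × √(2/52) = 0.636. The two-sided t-test gives 0.642. A Mann-Whitney test would give 0.657, and a one-sided test 0.574–0.578. I use 0.642.

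**Step 2: false contrast when the effect is the same in everyone.** Let pA and pB be the t-test powers in the two subgroups. The chance that exactly one is significant is pA(1 − pB) + pB(1 − pA). At d = 0.642:

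| Split per arm | pA | pB | Exactly one significant |
|---|---|---|---|
| 26/26 | 0.622 | 0.622 | 2 × 0.622 × 0.378 = 47% |
| 36/16 | 0.766 | 0.420 | 0.766 × 0.580 + 0.420 × 0.234 = 54% |
| 42/10 | 0.828 | 0.274 | 0.828 × 0.726 + 0.274 × 0.172 = 65% |

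Simulation with 40,000 runs gave 47.2%, 54.0% and 65.3%.

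**Step 3: sensitivity to the assumed common effect.**

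| d | 26/26 | 36/16 | 42/10 |
|---|---|---|---|
| 0 | 9.5% | 9.5% | 9.5% |
| 0.4 | 41% | 43% | 46% |
| 0.5 | 49% | 52% | 58% |
| 0.642 | 47% | 54% | 65% |
| 0.8 | 31% | 42% | 60% |
| 1.0 | 11% | 23% | 44% |

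**Step 4: no effect at all, several factors.** The plan does not say how many factors were examined. As an illustration, three random two-level factors (six CIs) give about a 21% chance that at least one CI excludes zero.

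**Step 5: what an interaction estimate would do.** In the same simulations, a treatment-by-subgroup test at two-sided 5% declared a false difference in 5.1%, 4.8% and 5.0% of runs. Its precision is limited. In SD units its standard error is √(2/nA + 2/nB), where nA and nB are the subgroup sizes per arm:

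| Split per arm | Standard error | Power for an interaction of 0.642 SD | Interaction detectable with 80% power |
|---|---|---|---|
| 26/26 | √(2/26 + 2/26) = 0.392 | 37% | 1.10 SD |
| 36/16 | √(2/36 + 2/16) = 0.425 | 33% | 1.19 SD |
| 42/10 | √(2/42 + 2/10) = 0.498 | 25% | 1.39 SD |

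**The case against.** A reader might infer that the plan adopts the fallacy outright and intends to read one significant and one non-significant subgroup as a difference in effect. The text does not support that. The subgroup clause shares a sentence with the intention-to-treat statement, and the comparison may well be with that result. The CI rule follows a sentence about differences between treatment arms, and nothing says how discordant subgroup results will be interpreted. Because estimates are shown with their CIs, a careful reader could also see the overlap. All of this stands: the plan is silent on subgroup inference rather than explicitly wrong.

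It does not remove the problem. The rule is unqualified and is the only one available for subgroup results. On the other reading, a subgroup that loses significance beside the overall result is still easily taken as showing no effect. At d = 0.642 a half-size subgroup misses significance 1 − 0.622 = 38% of the time.

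Two further objections also stand. The rates depend on an effect size, test and subgroup sizes that the plan does not state; a large common effect with equal halves, or no effect, brings the rate down to about 10%. And an interaction test is weak at this sample size, so it prevents false contrasts without being able to show that effects are alike.

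**Conclusion.** The point holds in a limited form. The plan reports subgroups, has a single rule that judges each CI alone, makes no exception for subgroups and offers no interaction estimate. If the rule is applied within subgroups, a spurious contrast between two of them has a probability of 47–65% at the back-solved effect of 0.64 SD, 41–58% at 0.4–0.5 SD, 31–60% at 0.8 SD, 11–44% at 1.0 SD and about 10% with no effect. These figures assume a common effect, a two-sided t-test and splits between 26/26 and 42/10 per arm.

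A reader should not conclude that the primary finding is in doubt: it rests on the overall comparison, and no subgroup appears among the listed outcomes. Nor do the documents show that any false subgroup claim has been made, since they contain no results.

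**What to change.** In Statistical analysis:

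1. Say what the subgroup results are compared with, and name the factors. Mark as post hoc any factor chosen after the data were seen.
2. State that the CI-excludes-zero rule does not apply within subgroups. Label all subgroups exploratory, and show within-subgroup differences with 95% CIs descriptively, without a significance label.
3. Wherever subgroups are compared, report the treatment-by-subgroup interaction with its 95% CI. This is the difference between the subgroup mean differences in change, for example from a linear model with treatment, subgroup and their product.
4. State that a non-significant interaction is not evidence of equal effects.
5. If patients scored on NPRS are compared with those scored on PAINAD, say that this mixes a difference in patients with a difference in instrument, because under Data Collection cognitive status decides which scale is used.

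**Cost.** No new data are needed. A simple model must be specified, since the plan has none, and the median-difference option would need its own approach. Fewer subgroup claims can be made, and the interaction estimates will be imprecise.

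### The primary comparison of change in pain names no baseline covariate; if a mean difference is reported, ANCOVA on the recorded baseline score would generally give a tighter interval, by an amount the documents do not fix

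*Combined protocol and SAP*

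**What the plan says.** The Outcomes section defines the endpoint: "The primary outcome of the study was the change in pain intensity from baseline to 20 minutes after the intervention". Under Data Collection, both scores needed for it are taken: "Pain scores were recorded by nurses, blinded to the treatment groups, just before to the initiation of therapy and 20 minutes post-treatment completion". Each patient is scored from 0 to 10 on either the NPRS or PAINAD, depending on the GCS and AMT-4 results.

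The Statistical analysis section gives the comparison: "The between-groups differences were calculated using the change of each group and reported as mean or median differences with 95% confidence intervals (CI"). It names no regression model and no covariate, and it leaves the choice between mean and median open. It also makes the interval the decision rule, "We considered differences statistically significant if the 95% CI did not cross zero", and states that "No data was missing for the primary outcome". The type 1 error is 5%.

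The Sample size estimation section says: "To demonstrate this difference with 90% power, we determined the sample size to be 52 for each group, totaling 104". It gives no effect size, SD or correlation.

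**The concern.** Subtracting the baseline score is not the same as adjusting for it. The change score uses baseline, but with a coefficient fixed at 1. ANCOVA estimates the coefficient from the data. Unless the true slope is close to 1, the fixed coefficient over- or under-corrects for chance differences in baseline pain between the arms, and this adds variance.

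Precision is all that is at stake. There is no bias and the test is not invalid. Chance baseline imbalance is the source of the extra variance, and the unadjusted interval already allows for it, so it is not a second, separate harm. Precision still matters here because the plan decides significance by whether the 95% CI excludes zero. A wider interval than the data require therefore bears on the trial's conclusion.

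**Working it through.** **Inputs from the documents:** 52 per group (N = 104), 1:1 allocation, 5% type 1 error, 95% CI as the decision rule, baseline and 20-minute scores both recorded, no missing primary data.

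**Inputs the documents do not give, assumed here:** r, the correlation between baseline and 20-minute scores (0.3, 0.5, 0.7); k, the follow-up SD divided by the baseline SD (0.75, 1, 1.5); and, only to express widths in points, a baseline SD s0 = 2.

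**The plan's own figure.** The 52 per group cannot be reproduced, because no effect size or SD is stated. Solved backwards with a two-sided 5% t test and 90% power, it implies a standardised difference in change of 0.642. Sidedness is not stated for the sample size; one-sided sizing would imply 0.578. The CI widths below do not depend on either value.

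**Formulas.** Slope of the 20-minute score on baseline = rk.

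- Half-width for mean change: t(0.975, 102) × s0 × √[(1 + k² − 2rk) × 2/52]
- Half-width for ANCOVA: t(0.975, 101) × s0 × √[k²(1 − r²) × 2/52 × (1 + 1/100)]
- Large-sample variance ratio, ANCOVA to change: k²(1 − r²)/(1 + k² − 2rk) = 1 − (1 − rk)²/(1 + k² − 2rk)

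The ratio never exceeds 1 and equals 1 only when rk = 1. The factor 1 + 1/100 and the lost degree of freedom are the price of estimating the slope.

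**Worked case, k = 1, r = 0.5.** Change: 1.9835 × 2 × √(1.00 × 2/52) = 0.78. ANCOVA: 1.9837 × 2 × √(0.75 × 2/52 × 1.01) = 0.68. The reduction is 13.0%. The unadjusted N that would match ANCOVA with 104 is 104/(0.75 × 1.01) = 137.

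| k | r | slope rk | variance ratio | half-width, change | half-width, ANCOVA | CI narrower by | equivalent unadjusted N |
|---|---|---|---|---|---|---|---|
| 1 | 0.3 | 0.30 | 0.650 | 0.92 | 0.75 | 19.0% | 158 |
| 1 | 0.5 | 0.50 | 0.750 | 0.78 | 0.68 | 13.0% | 137 |
| 1 | 0.7 | 0.70 | 0.850 | 0.60 | 0.56 | 7.3% | 121 |
| 0.75 | 0.3 | 0.225 | 0.460 | 0.82 | 0.56 | 31.8% | 224 |
| 0.75 | 0.5 | 0.375 | 0.519 | 0.70 | 0.51 | 27.6% | 198 |
| 0.75 | 0.7 | 0.525 | 0.560 | 0.56 | 0.42 | 24.8% | 184 |
| 1.5 | 0.3 | 0.45 | 0.871 | 1.19 | 1.12 | 6.2% | 118 |
| 1.5 | 0.5 | 0.75 | 0.964 | 1.03 | 1.02 | 1.3% | 107 |
| 1.5 | 0.7 | 1.05 | 0.998 | 0.83 | 0.84 | −0.4% | 103 |

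**Power, if the trial was sized two-sided at 90% on change.** For r = 0.3, 0.5, 0.7, ANCOVA power at 52 per group is 97.9%, 96.1%, 93.8% (k = 1) and 93.3%, 90.7%, 89.8% (k = 1.5).

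**Simulation checks.** With 20,000 simulated normal trials per setting, the nine CI changes agree with the formulas within 0.05 percentage points. A second set used 3,000 trials per setting with integer scores truncated to 0–10. It assumed a baseline mean of 7, a control mean of 4.5, treated means of 2.5 to 3.6 before truncation, and an SD of 2. It gave 18%, 12%, 7% (k = 1), 30%, 25%, 21% (k = 0.75) and 9%, 3%, −0.4% (k = 1.5). Truncation moves the realised SD ratios to 1.00–1.05, about 0.8 and 1.31–1.45 respectively.

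**The case against.** The strongest reply is that nothing here is wrong. Endpoint, sample size and analysis all refer to the change score and agree with one another. The stated 90% power is for the difference in change, so leaving out ANCOVA does not lower the planned power. That is correct, and it makes this an efficiency point and not the correction of an error.

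The size also rests on no figure in the documents. The range runs from 32% narrower to 0.4% wider, nothing in the text favours one SD ratio over another, and the equivalent patient numbers restate the same assumptions. This stands. The direction is well founded, because ANCOVA is never less precise in large samples; whether the gain is material cannot be known from the plan. The table also assumes one common slope, while the scores mix two instruments, which adds uncertainty to figures already assumed.

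The plan allows a median difference, and the figures do not carry over to it directly. In that case ANCOVA would change the summary measure as well as the interval. The point is therefore confined to a mean difference.

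Finally, the past tense and a recruitment period ending in December 2024 suggest that the data are in. An adjusted analysis could then only supplement the planned one, and the width of the planned CI would stay as it is. This limits the benefit but does not remove it: readers would see a second, usually tighter estimate and how far baseline imbalance moves the result.

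**Conclusion.** The concern holds. The plan records baseline pain but names no covariate, and a mean difference in change is generally estimated less precisely than it could be. With 52 per group and the assumed correlations of 0.3 to 0.7, the 95% CI could be 7% to 19% narrower with equal SDs and 25% to 32% narrower if follow-up scores vary less than baseline scores. There is essentially no gain where the slope is near 1. The largest loss in the range is a CI 0.4% wider. The planned comparison remains valid and unbiased. The change is worth making because it is cheap and bears on the interval used for the decision, but the result does not depend on it for its validity.

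**What to change.** Fit a linear model for the 20-minute score with treatment and baseline pain as terms; modelling the change instead gives the same treatment estimate. Report the adjusted mean difference with its 95% CI beside the planned unadjusted comparison. The pain instrument (NPRS or PAINAD) may be added as a second covariate; it can be inferred from GCS and AMT-4 by the rule under Data Collection. If the data are already unblinded, label the model a post hoc sensitivity analysis and do not let it replace the planned result.

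The cost is low, since baseline pain is already recorded. Estimating the slope costs about 0.5% of CI width for one covariate and 1.0% for two. If a median was intended as the primary summary, the adjusted result is on a different measure, and the report should say so.
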